#### **Pharmacokinetic Concentrations**

To assess the PK profile of PF-06747143, total antibody and unconjugated payload, PK concentrations will be listed, summarized and plotted for subjects in the PK analysis set (as defined in Section 7.3) Presentations for PF-06747143, total antibody and unconjugated payload will include:

- a listing of all concentrations sorted by dose, subject ID, day and nominal time post dose. The listing of concentrations will include the actual times. Deviations from the nominal time will be given in a separate listing.
- a summary of concentrations by dose, day and nominal time post dose, where the set of statistics will include n, mean, median, standard deviation, coefficient of variation (cv) and the number of concentrations above the lower limit of quantification.
- a plot of mean concentrations against nominal time postdose by dose (based on the summary of concentrations by dose and time postdose), preferably with all doses also on the same graph.
- a plot of median concentrations against nominal time postdose by dose (based on the summary of concentrations by dose and time postdose), preferably with all doses also on the same graph.
- a log-linear plot of mean concentrations against nominal time postdose by dose (on the same plot), preferably with all doses also on the same graph.
- a log-linear plot of median concentrations against nominal time postdose by dose (on the same plot), preferably with all doses also on the same graph.
- plots (linear and log scale) of individual concentrations against actual time postdose.

The length of time used for the x-axes of these plots will be decided on review of the data, and will depend on how long PK concentration is quantifiable in the matrix.

In addition to the above, a median plot (linear and log scale) of the predose concentrations at each cycle against day will be provided for each dose, on the same plot, in order to assess the attainment of steady-state. Individual subject profiles will also be plotted.

For summary statistics and mean/median plots by sampling time, the nominal PK sampling time will be used, for individual subject plots by time, the actual PK sampling time will be used.

#### 9.2.3. Safety Analyses

#### **Adverse Events**

Adverse Events (AEs) will be graded by the investigator according to the CTCAE version 4.0 and coded using the MedDRA. The focus of AE summaries will be on Treatment Emergent Adverse Events, those with initial onset or increasing in severity after the first dose of study medication. The number and percentage of patients who experienced any AE, serious AE (SAE), treatment related AE, and treatment related SAE will be summarized according to worst toxicity grades. The summaries will present AEs both on the entire study period and by cycle (Cycle 1 and Cycles beyond 1). The Safety Analysis Set will be used.

#### **Laboratory Tests Abnormalities**

The number and percentage of patients who experienced laboratory test abnormalities will be summarized according to worst toxicity grade observed for each laboratory test. The analyses will summarize laboratory tests both in the entire study period and by cycle (Cycle 1 and Cycles beyond 1). Shift tables will be provided to examine the distribution of laboratory abnormalities. The Safety Analysis Set will be used.

For laboratory tests without CTC grade definitions, results will be categorized as normal, abnormal high/low or not done.

#### Other Variables: Immunogenicity

The development of anti PF 06747143 antibodies will be measured using validated assays. Listings and summary tabulations of the anti PF 06747143 antibody data at baseline and post randomization will be generated.

Potential impact of immunogenicity on PK and clinical responses including safety/tolerability and efficacy of PF 06747143 will be explored, if data is warranted.

#### 9.2.4. Standard Analyses

#### **Study Conduct and Patient Disposition**

An accounting of the study patients will be tabulated. The subject evaluation groups will be listed. The Full Analysis Set will be used.

Subject discontinuation from treatment and study will be tabulated and listed separately with their reason for discontinuation. The Safety Analysis Set will be used.

#### **Baseline Characteristics**

Baseline characteristics such as demographics, prior medication, medical history, ECOG performance status, and primary diagnosis will be tabulated and listed. For ECOG performance status a shift table (worst post-baseline vs baseline may be produced). The Safety Analysis Set will be used.

#### **Treatment Administration/Compliance**

Listings and tables by dose level will be provided. Cycle length is 21 days. Day 1 of a cycle is the first date of dose within that cycle. The safety analysis set will be used.

Dose modifications may occur in the following ways:

- Cycle delay—Day 1 of current cycle starts later than 21 days from Day 1 of the previous cycle (only applies to cycle 2 and above);
- Dose reduction—A decrease in the administered total daily dose (non-zero) compared to the planned total daily dose upon enrollment. If in the CRF the prescribed dose unit is mg/kg, but the actual dose is in mg the actual dose mg/kg should be calculated considering the body weight of the patient at that visit.

Intra-patient dose escalation is not allowed in this study. The following will be summarized by subject for each dose level:

- Number of subjects per dose level;
- Median and range of number of cycles started per subject;
- Number (%) of subjects starting a cycle (1, 2, 3...);
- Number (%) of subjects with cycle delays;
- Number (%) of dose interruptions (include both known and unknown dates);
- Number (%) of subjects with dose reductions:
- Number (%) of each reason (AE vs. Other) for cycle delays, dose interruptions and dose reductions;

• Time on treatment (median, range).

The following will be summarized by cycle received for each dose level:

- Total number of cycles started;
- Number of cycles started per subject (median, range);
- Number of cycles before 1st delay (median, range);
- Number of cycles before 1st reduction (median, range);
- Number of cycles before 1st interruption (median, range).

The following will be summarized for cumulative dose by dose level and cycle:

• Summary statistics (mean, median, standard deviation and range) of cumulative dose and percent of starting dose (compared to Day 1 dose of each cycle)

Listings by subject (ordered by dose level): start date and stop date of each dosing period within each cycle (including records with 0mg), administered total daily dose for each period, any missed doses with unknown dates (Y/N), number of missed doses with unknown dates, reason for any dosing changes.

Listings by subject and each cycle (ordered by dose level): cycle length, total planned dose, administered total dose, percentage of planned dose, dose delay (yes/no), dose reduction (yes/no), and dose interruption (yes/no).

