#### 2.1. Study Overview

PF-06747143 will initially be developed in patients with acute myeloid leukemia (AML). The diagnosis of AML will be according to the World Health Organization (WHO) classification (Ref (8). The study will be conducted in two parts, Part 1 single agent dose escalation and Part 2 PF-06747143 in combination with standard chemotherapy with an option for single agent cohort expansion at the RP2D.

Assessment of anti-leukemia activity of PF-06747143 will be based on Diagnosis and management of acute myeloid leukemia in adults: recommendations from an international expert panel, on behalf of the European LeukemiaNet. (Ref (2).

#### 2.1.1. Part 1

Part 1, dose escalation, is an open-label, multi-center, single arm, non randomized, multiple dose, safety, pharmacokinetic and pharmacodynamic study of single-agent PF-06747143 in sequential dose levels of adult patients with refractory and/or relapsed AML in order to establish MTD/ RP2D or maximally permitted dose (MPD).

Patients will receive PF-06747143 as a weekly infusion (QW) in 28 day cycles at escalating doses. The proposed dosing scheme includes 0.3, 1.0, 3.0, 10, 15, and 20 mg/kg. Patients enrolled in the first two dose levels (0.3 mg/kg and 1.0 mg/kg) will be required to stay in the clinic/hospital overnight (minimum of 24 hours) after receiving the first dose of PF-06747143 to monitor for the potential risk of hyperleukocytosis that might be caused by the inhibition of by PF-06747143. On an individual basis, patients may be monitored overnight for the additional doses in Cycle 1 at the treating physician's discretion.

[figure not shown]
In the first three dose levels (ie, starting dose 0.3 mg/kg through 3.0 mg/kg), initiation of the first dose of PF-06747143 for each patient in the dose level must be at least 72 hours after the first dose of the previous patient. Patients enrolled in subsequent dose levels will be treated on an outpatient basis with no staggering of patients unless there are safety concerns based on findings at the lower doses.

Once MTD or MPD is identified, additional patients may be enrolled at that dose level (to a minimum of 9) to further investigate the anti-leukemia activity, safety, and PK profile of PF-06747143 prior to an expansion cohort with single agent PF-06747143 at the MTD/MPD/RP2D.

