#### 2.1.1.1. Starting Dose

The starting dose will be 0.3 mg/kg, administered QW in 28 day cycles.

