Part 2 will assess the safety and tolerability and preliminary anti-leukemia activity of PF-06747143. In Part 2, PF-06747143 will be administered at 10 mg/kg QW (Section 3.1.2.1) on 28 day cycles in combination with chemotherapy in two separate cohorts each containing up to 30 patients with newly diagnosed AML, including Cohort 1 in fit treatment naïve AML patients, in which PF-06747143 will be combined with standard intensive 7+3 chemotherapy with cytarabine (100-200 mg/m2 continuous infusion for 7 days) and daunorubicin (60-90 mg/m2 daily for 3 days), and Cohort 2 in unfit treatment naïve AML patients who are considered to not tolerate or decline to receive standard intensive 7+3 treatment, in which case PF-06747143 will be combined with standard dose of azacitidine (75 mg/m2 administered subcutaneously or intravenously daily for 7 days) or decitabine (20 mg/m2 by continuous intravenous infusion over 1 hour daily for 5 days in a 4-week schedule) based on drug availability and institutional guidance.

Attributions to fit or unfit in Part 2 will be based on "Consensus-based definition of unfitness to intensive and non-intensive chemotherapy in acute myeloid leukemia: a project of Italian SIE, SIES and GITMO group on a new tool for therapy decision making"25 per Investigator judgement.

An additional single agent PF-06747143 expansion cohort, Cohort 3, at the MTD/RP2D may be initiated in Part 2 in 15-30 refractory and/or relapsed AML patients based on single agent PF-06747143 clinical benefit in Part 1.

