#### 6.2. 'PER PROTOCOL' Analysis Set

The per protocol analysis set includes all enrolled patients who receive at least one dose of study treatment at the dose level of MTD and who do not have major treatment deviations during first cycle. Patients with major treatment deviations in Cycle 1 are not evaluable for the MTD assessment and may be replaced. Major deviations include failure to satisfy major entry criteria (eg, confirmation of the target disease population; signed informed consent), administration of less than 3 out of the 4 doses in Cycle 1 or 80% of the planned Cycle 1 dose (provided that the reduction is not due to toxicity attributable to PF-06747143) or use of

other anti-cancer/anti-leukemia treatments during the active treatment and disease follow up phases other than as defined/allowed in this protocol.

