#### 7.2. Safety Endpoints

#### 7.2.1. DLT Definitions

A DLT will be classified according to NCI CTCAE version 4.03 and is defined as any of the following adverse events unless the event can clearly be determined to be unrelated to drug occurring in the first cycle of treatment (within 28 days of first dose or until patient receives a second cycle if there are treatment delays). Data from all cycles of treatment will be analyzed for safety, delayed toxicity, and cumulative toxicity.

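### SAP Section 9.2.4 measures cycle delay against a 21-day cycle, but the SAP's schedule has 28-day cycles, so every on-schedule start from Cycle 2 on is flagged as delayed

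*SAP*

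**What the plan says.** Section 9.2.4 (Treatment Administration/Compliance) gives the figure twice. It first states "Cycle length is 21 days". It then defines a cycle delay, for Cycle 2 and above, as the case where "Day 1 of current cycle starts later than 21 days from Day 1 of the previous cycle". Day 1 is the date of the first dose in the cycle. The definition feeds planned outputs by dose level, among them "Number (%) of subjects with cycle delays".

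The treatment schedule in the same document differs:

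- Section 2.1.1 (Part 1): "Patients will receive PF-06747143 as a weekly infusion (QW) in 28 day cycles at escalating doses".
- Section 2.1.1.1: "The starting dose will be 0.3 mg/kg, administered QW in 28 day cycles".
- Section 2.2 (Part 2, Cohorts 1 and 2): weekly dosing "on 28 day cycles in combination with chemotherapy".
- Section 6.2 counts as a major deviation "administration of less than 3 out of the 4 doses in Cycle 1", so Cycle 1 holds four doses.
- Section 7.2.1 sets the first-cycle DLT window as "within 28 days of first dose or until patient receives a second cycle". Its hematologic criterion places the end of Cycle 1 at about day 28 to 32.

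No section gives a 21-day schedule for any cohort. Section 2.2.2.4 states no cycle length for the optional single-agent Cohort 3.

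**The concern.** The 21-day figure is part of the rule a programmer would code. If the planned interval between consecutive Day 1s is 28 days and the delay threshold is 21, the flag is set for patients who are on time. It then cannot separate them from patients who are really late.

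This matters because Part 1 is meant to describe tolerability at increasing doses, and cycle delay by dose level is one of its descriptive measures. Under the rule as written, near-universal delay would appear at every dose among patients who reach Cycle 2, and any real pattern across doses would be hidden. If the percentage is taken over all patients at a dose level, it becomes in effect the percentage who started Cycle 2. A dose at which many patients stop early would then show fewer delays.

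**Working it through.** **Inputs**

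- Delay threshold: gap between consecutive Day 1s greater than 21 days (Section 9.2.4).
- Planned gap: 28 days (Sections 2.1.1, 2.1.1.1 and 2.2).
- Dosing interval: 7 days; doses in Cycle 1: 4 (Section 6.2).
- Longest stated course: about 12 cycles in 1 year (Section 2.2.2.2, Cohort 2).

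**Step 1. Can the 21-day figure be recovered from the rest of the SAP?**

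- Four weekly doses span 4 × 7 = 28 days; 21 days would hold only 21 / 7 = 3. The four doses fall on Days 1, 8, 15 and 22, and Day 22 lies outside a 21-day cycle.
- The first-cycle DLT window is 28 days.
- Twelve cycles last 12 × 28 = 336 days or 12 × 21 = 252 days. Against a stated year, the first is a rough fit and the second is not. This is weak support, because the SAP marks the 12 as approximate.

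The figure cannot be recovered. Every other statement about the schedule agrees with 28 days.

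**Step 2. Apply the rule.** A start is flagged when gap > threshold.

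| Gap between Day 1s (days) | Position against the 28-day schedule | Flagged, threshold 21 | Flagged, threshold 28 |
|---|---|---|---|
| 21 | 7 days early | no | no |
| 22 | 6 days early | yes | no |
| 27 | 1 day early | yes | no |
| 28 | on time | yes | no |
| 29 | 1 day late | yes | yes |
| 35 | 7 days late | yes | yes |

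With the threshold of 21, the answer is the same for all gaps from 22 days upward.

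**Step 3. Follow one patient.** A patient exactly on a 28-day schedule for 12 cycles has 12 − 1 = 11 eligible starts (Cycles 2 to 12), each with a gap of 28 days. Threshold 21 flags 11 of 11; threshold 28 flags 0 of 11. Twelve cycles is the Cohort 2 maximum and serves only as an illustration: a single on-time Cycle 2 is enough to count the patient as delayed.

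**Step 4. Trace the outputs.**

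- Subjects with cycle delays: all patients who start Cycle 2 on or after the scheduled day are counted, 100% of them, whether the true delay rate is 0% or 100%.
- Cycles before the first delay: always 1 for these patients, if completed cycles are counted.
- Reasons for delay (AE or other): a reason is called for where no delay occurred. How far this distorts the table depends on how flagged cycles with no recorded reason are classified, which the SAP does not say.
- By-cycle listing: it carries a yes/no item for dose delay. The SAP does not define that term separately. If it is the same flag, it is wrong in the same way.

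Cycles started, time on treatment, cumulative dose, reductions, interruptions, DLT counts, mTPI decisions and the per-protocol set do not use the 21-day figure.

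**The case against.** The strongest reply concerns weight, since the contradiction itself is plain. The affected tables are descriptive, in a non-randomized study without hypotheses. A delay rate near 100% among patients reaching Cycle 2 would be conspicuous when the tables are reviewed. The listings include cycle lengths and dosing dates, so the delays could be recomputed. AE-related delays might still be countable in the reasons table if reasons come from collected data. The delay item in the by-cycle listing is not expressly tied to the cycle-delay definition.

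Much of this stands. The effect on the reasons table and on the listing is an inference, and nothing here touches dose finding. It does not rescue the two outputs that follow directly from the definition, the count of subjects with delays and the cycles before the first delay. Both are wrong if the SAP is followed. Relying on someone to notice is a poor substitute for a correct rule, and Section 2 of the SAP would require the departure to be described in the study report. Nor can the point be left to the protocol, because the conflict lies wholly within the SAP.

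**Conclusion.** The concern holds. For Part 1 and the Part 2 combination cohorts, the delay rule in Section 9.2.4 contradicts the SAP's own schedule and flags every on-schedule start from Cycle 2 on. The count of subjects with cycle delays and the cycles before the first delay carry no information about real delay; the reasons table and the by-cycle listing are probably affected as well. The conclusion assumes that patients are treated on the 28-day schedule stated in Sections 2.1.1, 2.1.1.1 and 2.2 and that the rule is programmed as written. It does not extend to Cohort 3, for which the SAP gives no cycle length. It should be corrected before the tables are programmed, but it does not affect the primary safety conclusions.

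**What to change.** Reconcile Section 9.2.4 with Sections 2.1.1, 2.1.1.1, 2.2, 6.2 and 7.2.1, so that both the cycle length and the delay threshold used in the analysis equal the cycle length of the planned schedule. If any cohort has a different cycle length, tie the threshold to that cohort's own schedule. It would also help to say whether the delay item in the by-cycle listing is the same flag.

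The cost is two numbers in Section 9.2.4 and the matching line of the programming specification. No data collection and no other analysis changes.

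### Dose reductions are counted with no tolerance and without a prescribed change, so rounding or weight gain alone can be tabulated as a reduction

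*SAP*

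**What the plan says.** SAP Section 9.2.4, under Treatment Administration/Compliance, lists cycle delay and dose reduction as the ways a dose can be modified. A dose reduction is "A decrease in the administered total daily dose (non-zero) compared to the planned total daily dose upon enrollment". The comparator is fixed at enrollment, and the only qualifier on the administered dose is that it is not zero.

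A conversion follows, with a condition: "If in the CRF the prescribed dose unit is mg/kg, but the actual dose is in mg", then "the actual dose mg/kg should be calculated considering the body weight of the patient at that visit".

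The resulting flag feeds several outputs by dose level:

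- "Number (%) of subjects with dose reductions";
- "Number (%) of each reason (AE vs. Other) for cycle delays, dose interruptions and dose reductions";
- the median and range of cycles before the first reduction;
- a yes/no entry for each subject and cycle in a listing, which also gives the percentage of planned dose.

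Section 2.1.1 sets the dosing frequency: "Patients will receive PF-06747143 as a weekly infusion (QW) in 28 day cycles at escalating doses". The planned levels run from 0.3 to 20 mg/kg. The one dose-percentage margin in the SAP, 80% of the planned dose, appears in Sections 6.2, 6.6 and 7.2.1. It governs major deviations and evaluability, not dose reductions.

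**The concern.** A dose-reduction table is meant to show how often treatment had to be lowered. This definition instead tests whether a computed mg/kg value is below the planned one by any amount. The planned value is fixed, but the divisor moves with each visit's weight, and an infusion in whole milligrams rarely matches the exact product of dose level and weight. A patient whose prescribed dose never changed can be counted as reduced.

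With weekly infusions there are several chances for a flag in each cycle, and one is enough to enter the subject count and fix the cycle of first reduction. The tables are read across dose levels. An artefact whose frequency depends on the dose level can therefore create or mask a pattern that looks like tolerability.

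**Working it through.** The SAP gives no figure for the share of subjects flagged, so there is nothing to reproduce. The check asks whether the rule can flag an unchanged dose, and how often.

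**Single infusions** (weights assumed; flag if administered mg ÷ visit weight is below the planned mg/kg)

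- Weight gain, dose set from baseline weight, 10 mg/kg: 75.0 kg gives 750 mg. At 75.2 kg, 750 ÷ 75.2 = 9.97 mg/kg, so it is flagged.
- Rounding, dose set from visit weight, 0.3 mg/kg: 0.3 × 74.7 = 22.41 mg, given as 22 mg. 22 ÷ 74.7 = 0.2945 mg/kg, so it is flagged.
- Visit weight, 10 mg/kg: 10 × 74.7 = 747 mg exactly. Nothing is lost to whole-mg rounding, so there is no flag.

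**At least one flag in k infusions, if independent:** 1 − (1 − p)^k, where p is the assumed chance per infusion. Four weekly infusions make one 28-day cycle (Section 2.1.1).

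| p | k = 4 | k = 8 |
|---|---|---|
| 0.50 | 93.8% | 99.6% |
| 0.25 | 68.4% | 90.0% |
| 0.10 | 34.4% | 57.0% |

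**Simulation without the independence assumption.** There were 40,000 patients per scenario. Every input is assumed: weight mean 75 kg, SD 15, recorded to 0.1 kg; weekly weight change SD 1% with mean −1%, 0 or +1%. No patient has a true reduction.

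| Assumed practice, zero tolerance | 4 infusions | 8 infusions |
|---|---|---|
| Visit weight, no rounding or rounded up, any level | 0% | 0% |
| Visit weight, nearest mg, 0.3 to 3 mg/kg | 85–91% | 96–99% |
| Visit weight, nearest mg, 10 or 20 mg/kg | 0% | 0% |
| Baseline weight, 10 mg/kg, no drift | about 67% | about 78% |
| Baseline weight, 10 mg/kg, gain 1% a week | 98% | 99.9% |
| Baseline weight, 10 mg/kg, loss 1% a week | 18% | 18% |

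The no-drift row can be checked by hand. For a symmetric random walk, the chance of exceeding the starting weight at least once in m weekly steps is 1 − C(2m, m) ÷ 4^m. With m = 3 (four infusions) this is 1 − 20/64 = 68.8%; with m = 7 it is 1 − 3432/16384 = 79.1%. The simulated values are slightly lower because weights recorded to 0.1 kg can tie.

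**Would a tolerance repair it?** Often, but not always.

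- Visit-weight dosing, 3 mg/kg, rounding to the nearest 10 mg, 4 infusions: about 84% flagged with zero tolerance, 0% with 5% or 10%.
- Baseline-weight dosing with 1% weekly gain, 8 infusions: a 5% tolerance still leaves about 76% flagged.
- 0.3 mg/kg rounded to the nearest 10 mg: a 10% tolerance still leaves about 33% flagged. For example, 22.41 mg given as 20 mg is 20 ÷ 22.41 = 89.2% of plan.

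**The case against.** The strongest reply is that the dosing weight, the rounding rule and the CRF units normally belong to the protocol, pharmacy manual and CRF, which are not at hand. If the mg dose is set from the visit weight, dividing by the visit weight is the correct conversion: it stops a lower mg dose after weight loss from being read as a reduction. The conversion is also conditional on the CRF units. And because the SAP asks for a reason for each reduction, a programmer might count only deliberate, recorded changes.

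Most of this stands as a limit on size. It does not repair the definition, which mentions neither intent nor a margin. Asking for a reason does not remove an artefact from the subject count or from the cycles before first reduction, because neither is described as split by reason.

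Three stronger readings are tempting, and the documents do not support them.

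- *Nearly every patient will be flagged.* The 94% and 99.6% figures require an independent 50% chance at each infusion. That is an assumption, and other plausible practices give 0% or 18%.
- *The choice of RP2D is compromised.* Section 7.2.4 rests the RP2D on Part 1 results and on whether the MTD is feasible for long-term administration. It does not name the reduction tables.
- *True reductions are hidden.* The AE-versus-Other split and the listings of administered dose, reason for change and percentage of planned dose keep AE-driven reductions identifiable.

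**Conclusion.** The point holds as a defect of definition. Section 9.2.4 lets rounding count as a dose reduction, and also weight gain where the mg dose comes from an earlier weight. No other section corrects this.

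The size cannot be fixed from the SAP. The false-flag share runs from 0% to about 100% across the assumed practices. Under one of them (visit weight, nearest mg) it is 85–91% after four infusions at 0.3 to 3 mg/kg and 0% at 10 and 20 mg/kg, so the artefact may differ by dose level. These shares rest on assumed weights, weight variation and rounding.

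The harm is confined to descriptive exposure output: the number and percentage of subjects with reductions, the cycles before first reduction and the yes/no listing. Cycle 1 DLTs, the mTPI decisions and the MTD do not use this flag.

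**What to change.** Redefine the flag in Section 9.2.4: count a dose reduction only when the CRF records an infusion prescribed below the patient's assigned mg/kg level, with a reason. Report every other shortfall through the percentage of planned dose, which the listing by subject and cycle already contains. The mg-to-mg/kg conversion at visit weight can stay for that percentage but should no longer trigger the flag.

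If a numeric tolerance is wanted as a back-up, prespecify it and make it allow for rounding at the lowest dose levels, since a flat 10% can still misflag at 0.3 mg/kg. It should not be the leading criterion. This is a counting rule for tables and leaves dosing untouched.

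The cost is a sentence or two in the SAP. Because the SAP already refers to a prescribed dose on the CRF and lists reasons for dosing changes, no new data should be needed, provided the CRF holds the prescribed dose for each infusion. The downside is that under-dosing nobody recorded as a reduction will appear only in the percentage of planned dose.

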#### 7.2.4. Recommended Phase 2 Dose (RP2D) Definition

The Recommended Phase 2 Dose (RP2D) is the dose chosen for further study based on Part 1 results. If the MTD proves to be clinically feasible for long term administration in a reasonable number of patients, such dose usually becomes the RP2D. Further experience with the MTD may result in a RP2D dose lower than the MTD.

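### Cycles before first dose reduction or interruption get a plain median and range with no rule for patients who never have the event, so first modification looks earlier than it is

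*SAP*

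**What the plan says.** All places are in the SAP, the only document at hand.

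- Section 9.2.4, Treatment Administration/Compliance, lists for each dose level "Number of cycles before 1st delay (median, range", "Number of cycles before 1st reduction (median, range" and the same pair of statistics for first interruption. The population is fixed by "The safety analysis set will be used".
- The same section also plans "Number (%) of subjects with dose reductions", matching counts for delays and interruptions, the reasons, the cycles started and "Time on treatment (median, range". Listings by subject and cycle flag delay, reduction and interruption.
- It does not say what value a patient without the event takes, or whether the median is limited to patients with the event.
- Section 9.1 assigns Kaplan-Meier to time-to-event endpoints. Section 8.2, under efficacy, refers to Appendix 2 for censoring. The Appendix 2 tables cover only progression-free survival, duration of response and time to progression, so no censoring rule reaches the dosing summaries.
- A cycle delay is defined as "Day 1 of current cycle starts later than 21 days from Day 1 of the previous cycle", whereas section 2.1.1 states "Patients will receive PF-06747143 as a weekly infusion (QW) in 28 day cycles at escalating doses".

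**The concern.** The number of cycles before a first reduction or interruption is a time to event. Section 2.1.1.2 keeps patients on treatment until progression, refusal or unacceptable toxicity, so many will leave without the event. The SAP names a statistic and a population that do not fit together: a plain median over the safety analysis set cannot be computed until someone decides what to do with those patients.

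The two obvious choices are to drop them or to give them the number of cycles they received. Both let early departure pull the median down. The reported timing then reflects partly how long patients stayed and only partly when the dose had to be changed. Planned treatment length also differs between Part 1 and the Part 2 cohorts, so the distortion need not be the same in each. What is at stake is the description of when modification first occurs.

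**Working it through.** The SAP states no figure for this summary, so there is nothing to reproduce. The check asks how far the two plain readings move the median.

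**Inputs.** The statistic and the population are from section 9.2.4. The per-cycle risk of a first reduction, h, and of leaving treatment, d, are not in the SAP. They are assumed as h = 5%, 10%, 20% and d = 10%, 20%, 30%, constant over cycles and independent of each other.

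**Formulas.** A reduction in cycle k counts as k − 1 cycles before it, and it is observed if the patient starts cycle k. Let s = (1 − h)(1 − d).

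- Share with an observed reduction: h / (1 − s).
- (a) Patients with a reduction only: median = ceil(ln 0.5 / ln s) − 1.
- (b) All patients, those without a reduction given their cycles received: P(value ≥ k) = (1 − h)^k (1 − d)^(k−1), and the median is the largest k at which this is at least 0.5.
- (c) Kaplan-Meier with those patients censored: median = ceil(ln 0.5 / ln(1 − h)) − 1.

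For h = 10%, d = 20%: s = 0.90 × 0.80 = 0.72. The share is 0.10 / 0.28 = 36%. For (a), ln 0.5 / ln 0.72 = 2.11, giving 3 − 1 = 2. For (b), k = 2 gives 0.81 × 0.80 = 0.648 and k = 3 gives 0.729 × 0.64 = 0.467, so the median is 2. For (c), ln 0.5 / ln 0.90 = 6.58, giving 7 − 1 = 6.

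All nine scenarios, which also agree with a simulation of 200,000 patients each:

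| h | d | Share with reduction | (a) | (b) | (c) |
|---|---|---|---|---|---|
| 5% | 10% | 34% | 4 | 5 | 13 |
| 5% | 20% | 21% | 2 | 3 | 13 |
| 5% | 30% | 15% | 1 | 2 | 13 |
| 10% | 10% | 53% | 3 | 3 | 6 |
| 10% | 20% | 36% | 2 | 2 | 6 |
| 10% | 30% | 27% | 1 | 2 | 6 |
| 20% | 10% | 71% | 2 | 2 | 3 |
| 20% | 20% | 56% | 1 | 2 | 3 |
| 20% | 30% | 45% | 1 | 1 | 3 |

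Both readings fall below (c) in every row. The smallest gap is 3 − 2 = 1 cycle and the largest is 13 − 1 = 12. At fixed h the share with a reduction falls as leaving rises (53%, 36%, 27% at h = 10%), so the crude percentage moves in the favourable direction.

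**Nine-patient example.** Suppose reductions occur in cycles 2, 3 and 5, and six patients without a reduction leave after cycles 1, 2, 3, 4, 6 and 8.

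- (a) Values 1, 2, 4: median 2, range 1 to 4. The patient with 8 unreduced cycles does not appear.
- (b) Values 1, 1, 2, 2, 3, 4, 4, 6, 8: median 3.
- (c) Survival is 7/8 = 0.875 at cycle 2, × 5/6 = 0.729 at cycle 3, and × 2/3 = 0.486 at cycle 5. The median is reached in cycle 5, that is after 4 cycles.
- Cumulative incidence of reduction over all nine: 1/9 = 11% by cycle 2, 2/9 = 22% by cycle 4, 3/9 = 33% by cycle 6. Discontinuation without a reduction: 2/9 = 22%, 4/9 = 44%, 5/9 = 56%.

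**Small levels.** Section 5 expects 2 to 4 patients at a typical level. If 33% ever have a reduction, a level of 3 has no value with probability 0.67³ = 0.30, and at most one with probability 0.30 + 3 × 0.33 × 0.67² = 0.75. At 15% these are 0.61 and 0.94.

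**Delay.** If a delay is counted from day 21 and cycles run 28 days, every patient who starts cycle 2 on schedule is delayed and scores 1. Only those who leave before cycle 2 have no value, so the mechanism above hardly operates.

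**The case against.** The strongest reply is that the median does not stand alone. The same list gives the number and percentage with each modification, the reasons, the cycles started and the time on treatment. Section 9.2.4 also tabulates discontinuations with reasons, and the listings allow any recalculation. There is no hypothesis test, and MTD decisions rest on DLTs. All of this stands, and it keeps the point small. It does not give the median a defined value.

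Four stronger readings are tempting, and the SAP does not support them.

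- A reader might infer that tolerability will look worse. Frequency is reported separately, and early leaving lowers the crude percentage. The distortion is in timing.
- A reader might infer that the plan drops patients without the event. It is silent, so the fault is a missing rule and not a chosen biased analysis.
- A reader might infer that dose selection rests on this median, because section 7.2.4 says "If the MTD proves to be clinically feasible for long term administration in a reasonable number of patients". That sentence names no statistic. Cumulative dose by cycle and the listings also describe when dosing changes.
- A reader might extend the argument to first delay. There the conflict over cycle length dominates.

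The remedy also has a fair criticism. Cumulative incidence still depends on how early patients leave. At h = 10%, incidence by cycle 6 is [h / (1 − s)] × (1 − s⁶), which gives 38%, 31% and 25% at d = 10%, 20% and 30%. It therefore does not make levels directly comparable, and it has to be read beside discontinuation.

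**Conclusion.** The point holds for first reduction and first interruption. The SAP fixes a plain median and range in a population where some patients have no value, and both plain readings place first modification too early relative to a censored estimate. Under the assumed rates the gap is 1 to 12 cycles, largest when reductions are rare and leaving is frequent. The direction was the same in all nine scenarios, but the size rests wholly on rates that the SAP does not give.

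The Kaplan-Meier comparator describes timing if nobody left. It needs leaving to be unrelated to the risk of reduction, which may fail when patients stop for toxicity. That is a reason to prefer cumulative incidence with a competing event as the remedy.

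Importance is low: the output is descriptive and has no role in the DLT or MTD rules. For first delay, the only conclusion is that the two cycle lengths contradict each other.

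**What to change.** In section 9.2.4:

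1. For first reduction and first interruption, replace the median and range with the cumulative incidence by cycle, for example at the end of Cycles 2, 4 and 6. Treat end of treatment for any other reason as a competing event, and use all treated patients at that dose level or cohort as the denominator. Show the cumulative incidence of discontinuation beside it.
2. Do this for the MTD level (at least 9 patients under section 5) and the Part 2 cohorts. For levels of 2 to 4 patients, rely on the listings already planned.
3. If any median is kept, label it as being among patients with the event, and give the number with the event over the number treated.
4. For first delay, first reconcile the 21-day cycle length in section 9.2.4 with the 28-day cycles in section 2.1.1.

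The cost is one programming change using dosing data already listed by subject and cycle. The output adds little at small dose levels.
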